9.3.4.2 Phase 2a (Dose Expansion)

Once the MTD and/or at least one RP2D is determined, enrollment of subjects into 1 of several expansion cohorts for selected tumor indications may begin at the RP2D. The SRC may select an RP2D that is below the MTD, or if an MTD is not reached, an RP2D may be selected by the SRC after careful review of all available clinical and laboratory data from Phase 1. The RP2D will not exceed the MTD.

The primary objective of the expansion phase is to determine preliminary efficacy as objective response (OR) using a Simon's two-stage design. The primary endpoint is based on the objective response assessed by local Investigator according to RECIST v1.1 (Eisenhauer et al., 2009; Schwartz et al., 2016). The primary analysis will take place once all subjects per cohort had at least 1 confirmed response assessment (ie, ≥ 12 weeks post-baseline) or have been withdrawn from the study.

9.3.5 Secondary Analyses

9.3.5.1 Phase 1 (Dose Escalation) & Phase 2a (Dose Expansion)

9.3.5.1.1 Efficacy Analyses

All efficacy analyses will be done for Investigator assessed RECIST v1.1 ([Eisenhauer et al., 2009](#); [Schwartz et al., 2016](#)), Investigator assessed iRECIST ([Seymour et al., 2017](#)), Central assessed RECIST v1.1 and Central assessed iRECIST. The local Investigator assessed RECIST is the primary endpoint for the Phase 2a.

9.3.5.1.1.1 Overall Response Rate

Overall response as defined by achieving confirmed CR and/or PR assessed by RECIST v1.1 will be presented by percentage rates and where appropriate the 95% confidence intervals (CIs). Partial or complete response needs to be confirmed with repeated assessment at least 4 weeks after the initial assessment. For changes in solid tumor size waterfall plots will be presented. For all response assessments swimmer plots will be presented. All response assessments will be listed.

9.3.5.1.1.2 Disease Control Rate at Month 3, 6, and 9

Disease control at months 3, 6, and 9, as defined by achieving CR and/or PR and/or SD assessed by RECIST v1.1 will be presented by percentage rates and where appropriate the 95% CIs. Waterfall plots will be presented.

9.3.5.1.1.3 Duration of Response

The DOR defined as time from first assessment of PR or CR to follow-on first assessment of progressive disease will be summarized by descriptive statistics including median DOR and where appropriate the respective 95% CIs. DOR will also be listed.

9.3.5.1.1.4 Progression Free Survival and Overall Survival

Time from first treatment received until disease progression or OS will be summarized by Kaplan-Meier estimates, median PFS/OS and where appropriate the respective 95% CIs. Subjects with no event will be censored at the last available tumor assessment for PFS and at the last timepoint known alive for OS.

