
	
Secondary Analyses
 
Phase 1 (Dose Escalation) & Phase 2a (Dose Expansion)
 
Overall response as defined by achieving confirmed complete response (CR) and/or partial response (PR) will be assessed by RECIST v1.1. DOR, PFS, and OS will be summarized using descriptive statistics and Kaplan-Meier estimates.
 
The PK analysis plan will be described in a separate Data Analysis Plan. Where feasible, non-compartmental analysis will be conducted using concentration-time data of AFM24. Summary statistics of PK parameters such as area under the concentration-time curve over the dose interval, maximum plasma concentration, time to maximum plasma concentration, and minimum plasma concentration, will be reported by dose group. Additional parameters or model-based analysis may be calculated depending on the available data.
 
In the expansion cohorts, owing to sparse data sampling an exploratory population PK analysis may be conducted to provide more comprehensive PK parameters for these subjects. If a population PK analysis is conducted, all available clinical PK data from AFM24 will be used.
 
Immunogenicity parameters will be summarized by descriptive statistics. Exploratory analyses will be summarized by descriptive or summary statistics. Potential relationships between dose, safety, PK, and exploratory PD endpoints will be examined. NK cells, macrophages, and molecular tumor markers will be examined for possible correlations with Investigator assessed RECIST efficacy endpoints where appropriate.
 
Interim Analyses
 
Phase 1 (Dose Escalation)
 
An interim analysis (IA) will be conducted at each dose escalation step. The BLRM will be updated with the respective number of subjects treated and the number of DLTs observed in the last cohort. The updated model will then give a statistical recommendation for the next escalation step. In addition, a risk-benefit assessment that includes a comprehensive analysis of safety and available clinical information will be done to decide on the next escalation steps.
 
In the event of a CTCAE Grade 5 AE or a second CTCAE Grade 4 AE at least possibly related to AFM24 at any time during Phase 1, the Sponsor will suspend further enrollment and an interim safety analysis will be done. The interim safety analysis will be reviewed by an ad-hoc SRC meeting to decide on further progression of the study.
 
At least 1 IA (end of Phase 1) will be performed after all subjects treated in Phase 1 have completed their first post-baseline disease assessment and its confirmation (2nd post-baseline assessment, i.e., ≥ 12 weeks post-baseline) or have withdrawn from the study. In case several RP2Ds will be determined, additional IAs might be performed after the respective dose level. No formal interim report will be written. All subjects still ongoing at this timepoint will continue until disease progression, intolerable toxicity, Investigator discretion, or subject's withdrawal of consent and all assessments will be included in final analysis at the end of study.
 
Phase 2a (Dose Expansion)
 
An IA, without a formal IA report, will be performed for each cohort independently, once the defined number of subjects (11, 15, and 15 subjects for Cohorts A, B, and C, respectively) in the respective cohort have completed a confirmed disease assessment or have withdrawn from the study. In case of a negative result, the respective cohort may be stopped for futility. The results of the IA will be non-binding. Safety criteria will also be evaluated to guide the decision to continue the study cohorts. During the conduct of the study, after the interim analysis of Cohort A and C and stopping these cohorts for futility, it was considered unlikely that the continuation criteria can be met

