7.7.3 ANALYSIS OF EXPLORATORY EFFICACY ENDPOINTS

Phase 1 (Dose Escalation)

Overall response rate (CR + PR) and disease control rate (CR + PR + SD), assessed by: Local iRECIST; Central RECIST v1.1 and Central iRECIST will be summarized.

In addition, Clinical Benefit Rate will be calculated and summarized. It will be defined similarly to DCR, but additionally requiring for SD to last at least 24 weeks.

Duration of Response (DOR) will be defined as (date of first progression or death – date of first response (unconfirmed))/30.4375. Patients without response will be excluded from the analysis. Patients without progression or death will be censored at the date of the last tumor scan.

Progression-Free Survival (PFS) will be defined as (date of first progression – date of first study drug injection)/30.4375. Patients without progression or death will be censored at the date of the last tumor scan.

Overall Survival (OS) will be defined as (date of death – date of first dose)/30.4375. Patients alive at the end of study will be censored on the last date of observation. Separate analyses for DOR and PFS will be created for local and central assessments. Censoring rules for all time-to-event endpoints can be seen in the table below.

Endpoint	Situation	Date	Censored/Event
Overall Survival	A death is recorded	Date of death	Event
Overall Survival	No death is recorded	Latest available observed date	Censored
Duration of Response	A PD is observed	First date of PD	Event
Duration of Response	No PD is observed, but there is a death recorded	Date of death	Event
Duration of Response	Neither PD nor Death are observed	Date of the last Tumor scan	Censored
Duration of Response	New anti-cancer therapy is started before any event is recorded	Date of the new anti-cancer therapy	Censored
Time to Response	A Response is observed	Date of the earliest (unconfirmed) response	Event
Time to Response	No Response is observed	Date of latest tumor assessment	Censored
Progression-Free Survival	A PD is observed	First date of PD	Event
Progression-Free Survival	No PD is observed, but there is a death recorded	Date of death	Event
Progression-Free Survival	Neither PD nor Death are observed	Date of the last Tumor scan	Censored
Progression-Free Survival	New anti-cancer therapy is started before any event is recorded	Date of the new anti-cancer therapy	Censored

PD = progressive disease

CONFIDENTIAL

Page 18 of 22

Statistical Analysis Plan template version 1.0 dated 27-MAR-2019

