9. DEVIATIONS FROM ANALYSIS AS DESCRIBED IN THE PROTOCOL

Apart from the above mentioned change, the planned analyses as described in this SAP do not deviate from the description in the protocol of the analyses to be performed.

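### The protocol's PFS and DOR wording and the SAP's PFS formula do not name death as an event, but the SAP's DOR formula and censoring rules do; the definitions must be aligned

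*Protocol*

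**What the plan says.** **Protocol, PFS (9.3.5.1.1.4).** PFS and OS share one sentence: "Time from first treatment received until disease progression or OS will be summarized by Kaplan-Meier estimates". The censoring rule follows: "Subjects with no event will be censored at the last available tumor assessment for PFS", with OS censored when the subject was last known alive. The word event is not defined, and death is not mentioned in connection with PFS.

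**Protocol, DOR (9.3.5.1.1.3).** DOR is the "time from first assessment of PR or CR to follow-on first assessment of progressive disease". Death is absent and no censoring rule is given, although the synopsis plans Kaplan-Meier estimates: "DOR, PFS, and OS will be summarized using descriptive statistics and Kaplan-Meier estimates".

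**SAP 7.7.3.**
- DOR counts death: "Duration of Response (DOR) will be defined as (date of first progression or death", measured from the date of first response.
- The PFS formula subtracts the first-dose date from the date of first progression. Death does not appear in it.
- The sentence directly after the PFS formula censors at the last scan only patients with neither progression nor death.
- The censoring table has a row "No PD is observed, but there is a death recorded" for both DOR and PFS. It is an event on the date of death.

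SAP 7.7.3 carries these rules into Phase 2a. There, protocol Table 2 lists DOR (local and central RECIST) and PFS (local and central) as secondary endpoints.

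**The concern.** Progression-free survival and time to progression are different quantities. The first counts death as a failure. The second, estimated by Kaplan-Meier with deaths censored, treats a death as if the subject could still have progressed later. A subject who dies before any post-baseline scan then adds nothing to the curve.

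The question is practical here. Subjects have pretreated, progressed disease, and protocol 1.8 cites their limited life expectancy. On the weekly schedule the first scan is in the last week of Cycle 2. Some deaths before a progression scan are plausible, and leaving them out can only make the curve look better. A programmer working from the SAP has a PFS formula and a PFS table that disagree. A reader working from the protocol cannot tell which quantity is meant.

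**Working it through.** **Step 1. The texts side by side**

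| Place | Endpoint | Is death without progression an event? |
|---|---|---|
| Protocol 9.3.5.1.1.3 | DOR | No; no censoring rule either |
| Protocol 9.3.5.1.1.4 | PFS | Not named; event undefined |
| SAP 7.7.3, DOR formula | DOR | Yes |
| SAP 7.7.3, PFS formula | PFS | No |
| SAP 7.7.3, censoring sentences and table | DOR and PFS | Yes |

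The DOR definitions conflict between the documents. The PFS definition is unclear in the protocol and contradictory inside the SAP.

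**Step 2. A small example that can be checked by hand**

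The documents give no PFS or DOR figure to reproduce. Take 15 invented subjects: progression in 6 at week 8, 3 at week 16, 2 at week 24 and 1 at week 32, and deaths without progression at weeks 5, 6 and 12.

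- *Death as an event:* after the two early deaths, survival is 13/15 = 0.867. At week 8 it is 0.867 × (1 − 6/13) = 7/15 = 0.467. Median: 8 weeks.
- *Progression only, deaths censored at the last scan:* the week 5 and 6 deaths are censored at time 0 and the week 12 death at week 8. At week 8, survival is 1 − 6/13 = 0.538. At week 16, with 6 at risk, it is 0.538 × (1 − 3/6) = 0.269. Median: 16 weeks.

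**Step 3. Size under assumed rates**

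Inputs:
- Scan days. The weekly schedule (protocol Table 11, note s) scans in the last week of Cycles 2 and 4 of 28 days, that is days 50–56 and 106–112. Midpoints: days 53 and 109.
- Assumed, not in the documents: exponential time to progression with median 75 days; independent deaths; a share d = 5%, 10% or 17% dead before day 53; no other censoring.

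*Progression only.* The curve at day 120 is the chance of no progression by the day 109 scan: 2^(−109/75) = 36.5%, whatever d is.

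*Death as an event, deaths only before the first scan:* 0.365 × (1 − d).

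*Death as an event, same death hazard continuing:* 0.365 × (1 − d)^(120/53).

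| d | Progression only | Deaths before first scan only (gap) | Hazard continues (gap) |
|---|---|---|---|
| 5% | 36.5% | 34.7% (1.8 points) | 32.5% (4.0 points) |
| 10% | 36.5% | 32.9% (3.7 points) | 28.8% (7.8 points) |
| 17% | 36.5% | 30.3% (6.2 points) | 23.9% (12.6 points) |

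The continuing-hazard column assumes more deaths than d suggests: about 8%, 16% and 27% have died without documented progression by day 120.

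*Median.* Progression only: 2^(−53/75) = 61.3% after the first scan and 36.5% after the second, so the median is day 109. With deaths only before the first scan and d = 17%, survival after that scan is 0.613 × 0.83 = 50.9%, so the median is still day 109. With a continuing hazard at d = 17%, the daily hazard is −ln(0.83)/53 = 0.0035, and the curve reaches 50% at day 53 + ln(0.509/0.5)/0.0035, about day 58.

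**Step 4. Cross-check under other assumptions**

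A simulation with scans at weeks 8, 16, 24 and 32 and then every 12 weeks, an assumed median of 2 or 4 months to true progression or death, and deaths as 10%, 20% or 30% of the total hazard gives these gaps in 16-week PFS:
- 2 months: 31.6 − 27.8 = 3.8, 35.9 − 27.8 = 8.1 and 41.1 − 28.0 = 13.1 points.
- 4 months: 56.5 − 53.0 = 3.5, 60.2 − 52.9 = 7.3 and 64.0 − 52.8 = 11.2 points.

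**The case against.** **The SAP already holds the right rule.** The sentence after the PFS formula and the censoring table both count death, and the SAP governs the analysis. This stands in part. A reader might infer that reported PFS will be biased upward, but the documents do not show that: an analysis run from the table counts these deaths. The overstatement arises only if the progression-only wording is followed.

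**The protocol never says that a death is censored.** This is correct. A reader might infer it by pairing progression with PFS and death with OS, but under a heading that names progression-free survival the phrase could also be loose drafting for progression or death. For DOR there is no censoring rule to apply. The defect is an unclear PFS definition and an incomplete DOR definition, not a stated rule to censor deaths.

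**SAP section 9 is weak evidence.** It says "the planned analyses as described in this SAP do not deviate from the description in the protocol", and a reader might take that as a false declaration. But the sentence opens by excepting a change that it does not identify. SAP section 1 also says the plan was written for protocol version 9.0 of 3 November 2022, whereas the protocol in hand cites a June 2023 guideline in its synopsis and records the early stop of Cohort B. The sentence cannot be tested against the present text.

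**No decision depends on it.** This also stands. ORR is the Phase 2a primary endpoint and alone drives the Simon thresholds. PFS and DOR are descriptive, without a test or power. Cohort B stopped at 8 subjects, and Cohorts A and C stopped for futility after interim analyses planned at 11 and 15, so any estimate will be imprecise under either rule.

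**Conclusion.** Wrong as written, and worth correcting. Protocol DOR and the SAP PFS formula leave death out, protocol PFS does not name it, and the SAP's DOR formula and censoring rules count it. Followed literally, the progression-only wording would overstate PFS and DOR relative to the SAP table whenever a subject dies before documented progression.

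The illustrative size at day 120 is about 2 to 6 points with deaths only before the first scan and about 4 to 13 points with a continuing hazard. This rests on the assumed 75-day median, the assumed 5% to 17% of early deaths, and independence of death and progression. No rate comes from the documents. The median may not move at all. With no such deaths the rules agree. The effect on DOR, which concerns responders only, was not quantified.

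**What to change.** - **Protocol 9.3.5.1.1.4:** separate PFS from OS. Define the PFS event as first documented progression or death from any cause, whichever is first. Keep last-assessment censoring for subjects with neither.
- **Protocol 9.3.5.1.1.3:** use the same event for DOR, and add the same last-scan censoring rule.
- **SAP 7.7.3:** change the PFS formula to first progression or death, so that it agrees with the censoring table.

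If a progression-only summary is also wanted, label it time to progression and report cumulative incidence with death as a competing event.

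The cost is a few sentences in the protocol and one SAP formula. No new data, sample size change or change to the primary analysis is needed. PFS and DOR come out the same as under the SAP table, and less favourable than under the progression-only wording if such deaths occur.

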9.3.5.1.2 Pharmacokinetic Analyses

The PK analysis plan for the assessment of AFM24 will be described in a separate Data Analysis Plan. Where feasible, non-compartmental analysis will be conducted using concentration-time data of AFM24. Summary statistics of PK parameters such as area under the concentration-time curve over the dose interval, maximum plasma concentration, time to maximum plasma concentration and minimum plasma concentration will be reported by dose group. Additional parameters or model-based analysis may be calculated depending on the available data.

In the expansion cohorts, owing to sparse data sampling population exploratory PK analysis may be conducted to provide more comprehensive PK parameters for these subjects. If a population PK analysis is conducted, all available AFM24 serum concentrations will be used.

9.3.5.1.3 Immunogenicity Analyses

Immunogenicity parameters will be summarized by descriptive statistics and listed.

9.3.6 Safety Analyses

9.3.6.1 Adverse Events

Adverse events, related AEs, SAEs and related SAEs, AEs with NCI CTCAE Grades ≥ 3 , AEs leading to premature discontinuation, interruptions or discontinuation of study drug, and standard medical queries will be analyzed descriptively utilizing corresponding Medical Dictionary for Regulatory Activities System Organ Classes and Preferred Terms. NCI CTCAE v5.0 toxicity Grades will be utilized for classifying severity.

Deaths within 28 days after the last dose and the corresponding reasons will be summarized. Also, all deaths overall will be summarized.

9.3.6.2 Safety Laboratory

Safety laboratory results will be graded by NCI CTCAE v5.0 if no grading exists values will be classified into low/normal/high based on laboratory normal ranges. Each parameter will be presented by descriptive statistics at each visit including change from baseline (Screening). Shift tables for CTCAE grades and normal ranges will be presented. All laboratory values will be listed. A separate listing for abnormal lab values (Grade 3 and higher, and low/high values) will be presented.

9.3.6.3 Vital Signs

Vital signs will be summarized by descriptive statistics at each visit including change from baseline will be presented and a listing will be provided.

9.3.6.4 Electrocardiogram

Local-read ECG data will be listed overall and a separate listing for any clinically significant finding in ECG values will be provided. The frequency and percentage of subjects with notable ECGs and newly occurring qualitative ECG abnormalities will be tabulated by cohort.

9.3.7 Exploratory Analysis

Exploratory biomarker analyses will be described in a biomarker statistical analyses plan.

Exploratory PD and biomarker analyses are dependent upon the availability of appropriate assays and may be deferred or not performed if, during or at the end of the study, it becomes clear that the analysis will have no scientific value or if there are not enough samples or responders to allow for adequate biomarker evaluation. If the study is terminated early or shows poor clinical efficacy, completion of biomarker assessments will be based on justification and intended utility of the data.

9.3.8 Interim Analyses

9.3.8.1 Phase 1 (Dose Escalation)

An interim analysis (IA) will be conducted at each dose escalation step. The BLRM will be updated with the respective number of subjects treated and the number of DLTs observed in the last cohort. The updated model will then give a statistical recommendation for the next escalation step. In addition, a risk-benefit assessment that includes a comprehensive analysis of safety and available clinical information will be done to decide on the next escalation steps.

In the event of a CTCAE Grade 5 AE or a second CTCAE Grade 4 AE at least possibly related to AFM24 at any time during Phase 1, the Sponsor will suspend further enrollment and interim

analysis will be done. The interim safety analysis will be reviewed by an ad-hoc SRC meeting to decide on further progression of the study.

At least 1 IA (end of Phase 1) will be performed after all subjects treated in Phase 1 have completed their first post-baseline disease assessment and its confirmation (2nd post-baseline assessment, ie, ≥ 12 weeks post-baseline) or have withdrawn from the study. In case several RP2Ds will be determined, additional IAs might be performed after the respective dose level. No formal interim report will be written. All subjects still ongoing at this timepoint will continue until disease progression, intolerable toxicity, Investigator discretion, or subject's withdrawal of consent and all assessments will be included in final analysis at the end of study.

9.3.8.2 Phase 2a (Dose Expansion)

An IA will be performed for each cohort independently, once the defined number of subjects (11, 15, and 15 subjects for Cohorts A, B, and C, respectively, – see [Table 10](#)) in the respective cohort have completed their first post-baseline assessment and its confirmation (2nd post-baseline assessment, ie, ≥ 12 weeks post-baseline) to be categorized under the primary response endpoint or have withdrawn from the study. Each cohort will be then assessed for futility. The results from this IA will be non-binding, unless no signs of efficacy are observed. Safety criteria will also be evaluated to decide on the continuation of the cohorts. During the conduct of the study, after the interim analysis for Cohort A and C and stopping these cohorts for futility, it was considered unlikely that the continuation criteria can be met in Cohort B. Hence it was decided to prematurely stop enrollment after 8 patients in Cohort B.

